5.11. Analysis of Anti-evinacumab Antibody Variables

The ADA variables described in Section 4.11 will be summarized using descriptive statistics by dose/cohort group in the ADA analysis set. Listings of ADA positivity and titers presented by patient, time point, and study treatment received will be provided. Prevalence of treatment-emergent ADA will be assessed as absolute occurrence (N) and percent of patients (%), grouped by study treatment received.

The influence of ADA on drug concentrations will be evaluated. Assessment of impact of ADA on safety and efficacy may be provided.

Anti-drug antibody status (negative or positive) and titer over the study duration may be classified as follows:

- Pre-existing immunoreactivity, defined as a positive ADA assay response at baseline, with all post-dose ADA results negative, or a positive assay response at baseline, with all post-dose ADA assay responses less than 9-fold over baseline titer levels.
- Treatment emergent - defined as any post-dose ADA positive response when baseline results are negative or missing. Treatment emergent ADA responses will be further classified into persistent, indeterminate and transient.
 - Persistent - A positive result in the ADA assay detected in at least 2 consecutive post baseline samples separated by at least a 16-week post baseline period [based on nominal sampling time], with no ADA-negative results in-between, regardless of any missing samples
 - Indeterminate - A positive result in the ADA assay at the last collection time point analyzed only, regardless of any missing samples
 - Transient - Not persistent or indeterminate regardless of any missing samples
- Treatment boosted - defined as any post-dose ADA response that is at least 9-fold over baseline titer levels when baseline results are positive

A second ad-hoc analysis set may also be generated that employs definitions as outlined in the Shankar et. al publication. Two sets of results will be presented in the Clinical Pharmacology report for the study, one using our definitions as provided in the SAP (Primary results) and one using the Shankar et. al definitions (Secondary or ad-hoc results). The primary results will be reported in the CSR.

- Titer category for subjects, by maximum ADA titer value:
 - Low (titer <1,000)
 - Moderate ($1,000 \leq \text{titer} \leq 10,000$)
 - High (titer >10,000)
- NAb status (positive or negative)
- Subgroup analysis of ADA data may be performed for Japanese patients when appropriate.

5.12. Analysis of Quality-of-life Variables

The summary of results for quality-of-life variables will be presented separately for the DBTP and OLTP, unless otherwise noted. Summaries for the DBTP will be presented by treatment groups (evinacumab, placebo) containing patients from the quality-of-life analysis set. Summaries for the OLTP will be presented by all patients and by treatment group in DBTP (i.e.,

evinacumab, placebo), for patients in the quality-of-life analysis set. No formal inferential testing will be performed for either period. Summaries will be descriptive in nature.

The baseline value is defined as the last available measurement prior to the date of the first double-blind study treatment administration (applicable to measurement derivations during both DBTP and OLTP).

EQ-5D

Individual EQ-5D items

Responses for each one of the 5 EQ-5D items will be summarized by patient frequency and percentage at baseline and each post-baseline visit. Responses are defined by 4 levels, specifically reporting level 1 (no problems), level 2 (some problems) and level 3 (extreme problems), and level 4 (not answered).

EQ-5D utility score

The observed value and the change from baseline of the utility score will be summarized using mean, median, Q1, Q3, SD, minimum and maximum for each post-baseline visit. Cumulative distribution functions for the change in utility score from baseline will be displayed at post-baseline visits.

HADS

The analysis of data from HADS instrument will be performed on the HADS quality-of-life analysis set.

The total score is the sum of the two sub-scores of anxiety and depression. Descriptive statistics (mean, median, Q1, Q3, SD, minimum and maximum) of the observed total scores and the change from baseline observed total scores will be summarized by visit.

6. DATA CONVENTIONS

The following analysis conventions will be used in the statistical analysis.

6.1. Definition of Baseline for Efficacy/Safety Variables

Unless otherwise specified, the baseline assessment is programmatically as the last available measurement prior to the date of the first double-blind study treatment administration. For patients randomized and not treated, the baseline value is defined as the last available value prior to the date of randomization.

6.2. Data Handling Convention for Efficacy Variables

Rules for handling missing data for primary and secondary efficacy variables are described in Section 5.7.1 and Section 5.7.2.

6.3. Data Handling Convention for Missing Data

Missing data will not be imputed in listings. This section includes the methods for missing data imputation for some summary analyses, if necessary.

Date and Time of First/Last Study Treatment

Since the study drug is administered at the site, the date and time of study drug administration are filled in e-CRF. No missing data is expected. Date of first/last administration is the first/last start date of study drug filled in e-CRF.

Adverse Event

If the intensity of a TEAE is missing, it will be classified as “severe” in the frequency tables by intensity of TEAEs. If the assessment of relationship of a TEAE to the investigational product is missing, it will be classified as related to the investigational product.

When the partial AE date/time information does not indicate that the AE started prior to study treatment or after the TEAE period, the AE will be classified as treatment-emergent.

Medication/Procedure

No imputation of medication/procedure start/end dates or times will be performed. If a medication date or time is missing or partially missing and it cannot be determined whether it was taken prior or concomitantly or stopped prior to the first study treatment administration, it will be considered as concomitant medication/procedure.

Potentially Clinically Significant Value (PCSV)

If a patient has a missing baseline value, this patient will be grouped in the category “normal/missing at baseline.”

For PCSVs with 2 conditions, one based on a change from baseline value and the other on a threshold value or a normal range, with the first condition being missing, the PCSV will be based only on the second condition.

For a PCSV defined on a threshold and/or a normal range, this PCSV will be derived using this threshold if the normal range is missing; e.g., for eosinophils the PCSV is >0.5 giga/L or $>ULN$ if $ULN \geq 0.5$ giga/L. When ULN is missing, the value 0.5 should be used.

Measurements flagged as invalid by the laboratory will not be summarized or taken into account in the computation of PCSVs.

6.4. Visit Windows

Visit windows will be programmatically imposed on those efficacy and safety measures repeatedly collected over the course of the study. These visit windows are derived from the number of days in study, specifically assigning day ranges to represent the study assessment schedule provided in the protocol. Data analyzed by time point (including efficacy, laboratory safety data, vital signs, ECG, quality of life, drug concentration and ADA) will be summarized using the analysis windows given in Appendix 10.2 (i.e. efficacy analysis windows for efficacy and global analysis windows for safety). These analysis windows will be applicable for all analyses, and they are defined to provide more homogeneous data for time point-specific analyses. If multiple valid values of a variable exist within an analysis window, the nearest from the targeted study day will be selected for analysis, unless otherwise specified. If the difference is a tie, the value after the targeted study day will be used. If multiple valid values of a variable

exist within a same day, then the first value of the day will be selected when time is available, else the scheduled visit will be selected.

6.5. Unscheduled Assessments

For efficacy, safety laboratory data, vital signs, ECG, ED-5D, and HADS, unscheduled visit measurements may be used to provide a measurement for a time point, including baseline, if appropriate according to their definitions. The measurements may also be used to determine abnormal values, AESIs, and PCSVs.

6.6. Pooling of Centers for Statistical Analyses

The randomization scheme was not stratified by center because the primary efficacy variable is centrally assessed and expected not to be influenced by the center when other factors such as diet are already controlled. Therefore, the center will not be added as factor in the primary analysis model.

6.7. Statistical Technical Issues

Not Applicable.

7. TIMING OF STATISTICAL ANALYSES

Efficacy and safety analyses for this study will be performed in two steps, specifically for patient data collected up to the time the last patient completes efficacy assessments at week 24 (step 1 consisting of the DBTP) and at the end of the study (step 2 for the OLTP). No formal interim analysis for efficacy is planned since analyses of primary and key secondary efficacy endpoints will be final at the time of first step analysis. Therefore, no multiplicity adjustment for multiple analyses is needed (see Section 5.7.2.5). The timing for patient data to be reported is defined below for each step:

- First step: efficacy analyses up to week 24 and interim safety analysis
 - This analysis will be conducted on all randomized patients when all patients will have all their lipid data up to week 24 efficacy analysis window collected and validated.
 - The efficacy analyses will be performed up to week 24 visit. Analyses of endpoints up to week 24 visit will correspond to the final analyses for these endpoints. Analysis of lipid parameters beyond week 24 visit will be descriptive.
 - The safety analyses will be performed on all safety data (double-blind and open-label) collected up to the common cut-off date. For this analysis, the common cut-off date is defined as date of the last week 24 visit.
- Second-step: final analysis
 - This analysis will be conducted at the end of the study and will consist of the final analysis of efficacy data at time points beyond the week 24 visit and final safety analysis.

Individuals involved in the first step analysis of the study will not be involved in the conduct of the study afterwards; individual patient identification will not be released to anyone who is directly involved in the conduct of the study. The first step analysis process, the measures used to protect the blind and the integrity of the study, the communication plan, and the confidentiality agreement will be described in a separate document. The results of the first analysis will not be used to change the conduct of the ongoing study in any aspect.

Analyses methods and conventions described in the other sections of this SAP will be applied for all analyses as applicable. The following additional rules will apply for analyses performed at first step analysis:

- Any lipid assessments within efficacy analysis windows up to the week 24 visit will be taken into account (may include few unscheduled lipid data soon after the cut-off date).
- Patients without end of treatment visit performed at the time of the cut-off date will be considered as ongoing and exposed up to the cut-off date. Therefore:
 - Patients who did not complete the respective treatment period nor prematurely discontinued the study treatment at cut-off date will be analyzed as “ongoing” in the disposition summary.
 - Their TEAE period and treatment period will end at the cut-off date.
 - Their treatment duration will be derived by considering date of cut-off as last administration date.
- Analyses of number of administrations, and mean administration frequency will be performed up to the last administration reported in the e-CRF up to the cut-off date.
- AEs occurring, worsening or becoming serious after the cut-off date will not be included in the analyses. However, any available outcome before database lock, regardless of timing in relation to the cut-off date, of an adverse event starting prior to the cut-off date will be taken into account. Medications, treatment discontinuations/completions and deaths occurring after the cut-off date will not be included in the analyses.
- Post-treatment period, and post-study period are not applicable for ongoing patients. Analyses of post-treatment AEs, post-study deaths and post-treatment medications will be performed for patients who either completed or prematurely discontinued the treatment before or at the cut-off date.
- Analysis of status at last study contact and proportion of patients with insufficient follow-up will be provided for patients who either completed or prematurely discontinued the treatment before or at the cut-off date.

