8.1.5. Early Termination Visit

In the case a patient prematurely discontinues study treatment, an unscheduled visit should occur with assessments normally planned at the (EOT) visit (it should take place within 5 days of treatment discontinuation, if possible). Patients who permanently discontinue study drug during the DBTP should then resume the original study schedule (except for study treatment administration) until end of the DBTP, and all efforts should be made to perform the week 24 assessments at week 24 (regardless of study treatment administration). All patients who prematurely discontinue study treatment (either in the double-blind period or the open-label period) should be followed for at least 24 weeks from the last dose of study drug, and a final end of study visit can take place with assessments as specified in the end of study visit (ie, follow up visit).

Sexually active WOCBP who discontinue the study prematurely should be reminded at the unscheduled visit following treatment discontinuation to maintain highly effective contraceptive measures for 24 weeks after the last dose of study drug. At this visit, the patient will be provided 5 urine pregnancy tests with instructions to test for pregnancy 4 weeks after this visit and Q4W thereafter. The patient will also be notified of Q4W follow-up phone calls to confirm continued contraception use and pregnancy reporting and to obtain the results of the urine pregnancy test.

If a WOCBP is lost to follow-up, sites should attempt a minimum of 2 telephone calls. If the patient cannot be reached on the second attempt, a formal letter will be issued from the site to the patient that reminds the patient of the importance of continued use of highly effective contraception use for at least 6 months after the last dose of study drug.

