4.5. Patient Disposition

Patient disposition will include the description of patient status at major milestone decisions in the study, as well as the patient analysis populations.

For patient study status, patient double-blind treatment period milestone categories are defined below. As applicable, percentages will be calculated using the number of randomized patients in the denominator, with two exceptions. Specifically, the two exceptions will be for the screened and non-randomized categories, which will not have associated percentages shown.

- The total number of screened patients, defined as originally having met the inclusion criteria and signed the ICF.
- The total number of randomized patients, defined as all screened patients with a double-blind treatment kit number allocated and recorded in the IVRS database, regardless of whether the treatment kit was used.
- The total number of patients randomized but not receiving study treatment.
- The total number of patients randomized and receiving study treatment.
- The total number of patients who completed the DBTP as collected on the end of double-blind treatment e-CRF.
- The total number of patients who completed the DBTP, defined as at least 20 weeks of study treatment exposure and visit week 24 performed.
- The total number of patients who prematurely discontinued study treatment during the double-blind period, and the reasons for discontinuation collected on the End of Double-blind Treatment e-CRF
- The total number of patients who do not proceed into OLTP and complete the last study follow-up visit (i.e. Follow-up week 20).

Patient OLTP milestone categories are defined below. As applicable, percentages will be calculated using a denominator of the number of patients administer open-label study treatment.

- The total number of patients receiving open-label study treatment.
- The total number of patients ongoing in OLTP (applicable for the first step analysis)
- The total number of patients who completed the OLTP as collected on the end of open-label treatment e-CRF.
- The total number of patients who completed the OLTP, defined as at least 44 weeks of study treatment exposure and week 48 visit performed.
- The total number of patients who prematurely discontinued study treatment during the OLTP, and the reasons for discontinuation collected on the End of Open-label Treatment e-CRF.
- The total number of patients from OLTP who complete the last study follow-up visit (i.e. Follow-up week 20).

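### SAP 7 uses two conflicting tests for who is ongoing at the first-step cut-off; read literally, one credits patients who have already left with exposure up to that date

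*SAP*

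**What the plan says.** SAP 7 fixes the first-step safety data at a single date: "For this analysis, the common cut-off date is defined as date of the last week 24 visit". Its additional first-step rules then begin: "Patients without end of treatment visit performed at the time of the cut-off date will be considered as ongoing and exposed up to" that date. Three items follow as consequences:

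- The first classes a narrower group as ongoing, for the disposition summary: "Patients who did not complete the respective treatment period nor prematurely discontinued the study treatment at cut-off date will be analyzed as" such.
- The second closes the safety periods: "Their TEAE period and treatment period will end at the cut-off date".
- The third sets exposure: "Their treatment duration will be derived by considering date of cut-off as last administration date".

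The next bullet takes the number and frequency of administrations only up to the last one recorded in the e-CRF. Later bullets reserve post-treatment events, deaths and medications for patients who completed or prematurely discontinued by the cut-off.

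Three other places bear on this. SAP 4.5 has a matching category among the open-label milestones, "The total number of patients ongoing in OLTP (applicable for the first step analysis", and none among the double-blind ones; it takes premature discontinuation from the end-of-treatment e-CRF. SAP 4.6 gives the exposure formulas, and SAP 4.8.1 the ends of the treatment and TEAE periods. Protocol 8.1.5 asks for an end-of-treatment type visit after early discontinuation and says of its timing: "it should take place within 5 days of treatment discontinuation, if possible".

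**The concern.** The opening sentence decides status by whether a visit took place; the first item decides it by treatment status. The two differ for exactly one kind of patient: someone who has left, by death, loss to follow-up or withdrawal, and never had the visit. By the opening sentence that patient is ongoing and exposed to the cut-off; by the first item the same patient has discontinued.

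The conflict is sharpest in the double-blind period. A patient still in it would have a later week 24 visit, which would move the cut-off. So no one is genuinely ongoing there, and the visit test, which names no period, can select only patients who have gone. In the open-label period the rule has a proper use, but the visit test also picks up anyone who died or was lost before the cut-off.

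At stake are the first-step exposure table and the treatment and TEAE period ends. Protocol 10.4.9.1 says this analysis may be used in a submission dossier. Two programmers could follow the same text and report different exposure for the same patient.

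**Working it through.** **Inputs.** Double-blind exposure in weeks = (last dose date + 28 − first dose date + 1)/7 (SAP 4.6). Doses run from day 1 to day 141, and week 24 is day 169 (schedule of events). The treatment period ends at last dose + 35 days. The double-blind TEAE period ends at last dose + 168 days for patients who do not enter the open-label period (SAP 4.8.1). Planned arms are 38 and 19 (SAP 2.2).

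**1. The plan's own figure.** A full course gives (141 + 28 − 1 + 1)/7 = 169/7 = 24.14 weeks, which agrees with the 24-week period.

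**2. Actual exposure of an early leaver.** Last dose at week 4 (day 29): (29 + 28 − 1 + 1)/7 = 57/7 = 8.14 weeks.

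**3. Same patient, opening sentence applied literally.** Suppose the patient was randomised t weeks before the patient who sets the cut-off. The cut-off is then that patient's study day 169 + 7t. With the cut-off as last dose, exposure = (169 + 7t + 28 − 1 + 1)/7 = 28.14 + t. If exposure simply stops at the cut-off, it is (169 + 7t − 1 + 1)/7 = 24.14 + t. Accrual is not given in the documents, so t is an assumption.

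| t (weeks) | cut-off as last dose | stopped at cut-off | actual |
|---|---|---|---|
| 0 | 28.14 | 24.14 | 8.14 |
| 26 | 54.14 | 50.14 | 8.14 |
| 52 | 80.14 | 76.14 | 8.14 |

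The first two columns do not depend on when dosing stopped. A leaver randomised after the patient who sets the cut-off (t negative) would get less than 28.14.

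**4. Visible inconsistency.** At t = 0 this patient moves from the SAP 4.6 category of 8 to under 12 weeks into the category of 20 weeks or more. The infusion count, taken from the e-CRF, stays at 2.

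**5. Period ends.** The standard treatment period ends on day 29 + 35 = 64; under the rule it ends on day 169 at t = 0. The standard TEAE period ends on day 29 + 168 = 197. At t = 0 the cut-off on day 169 comes first, so nothing changes. At t = 26 and 52 the rule gives day 351 and day 533 instead of 197.

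**6. Effect on an arm mean.** One such patient among 38 raises the mean by (28.14 − 8.14)/38 = 0.53 weeks at t = 0, 46/38 = 1.21 at t = 26 and 72/38 = 1.89 at t = 52. Among 19 the shifts double. That there is one such patient is an assumption.

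**7. Open-label example.** Last open-label dose on open-label day 29, with an assumed cut-off on open-label day 101. Actual: (29 + 28 − 1)/7 = 8.00 weeks. Under the rule: (101 + 28 − 1)/7 = 18.29 weeks.

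**8. First-item test instead.** A leaver recorded as discontinued is not ongoing and keeps 8.14 weeks (8.00 in the open-label example). The double-blind ongoing group is empty.

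**The case against.** The best defence is that the section corrects itself. The first item defines ongoing as neither completed nor discontinued. The next two items begin with a pronoun whose nearest antecedent is that group. The e-CRF identifies discontinuation without needing a visit, and later bullets treat discontinued patients separately. On that reading nothing goes wrong.

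This stands as a possible reading, and it rules out a stronger claim that a reader might infer: that the plan certainly gives departed patients impossible exposure. It does so only on the literal opening sentence. But the defence does not remove the conflict. The first item speaks only of the disposition summary, and nothing in it withdraws the statement that patients without the visit count as exposed to the cut-off.

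Other inferences are tempting and not supported:

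- *The early visit is optional.* In Protocol 8.1.5 the qualifier belongs to the 5-day timing; the visit itself should occur. Protocol 7.4.2 also keeps double-blind discontinuers on the visit schedule to week 24. The affected group is therefore small: deaths, losses, and withdrawals who do not return.
- *The Kaplan-Meier discontinuation curves are biased.* SAP 5.5 states no visit-based censoring.
- *Adverse-event rates are diluted.* SAP 5.8.1 reports n (%) over the safety set, so extra days for a dead or lost patient add no events and leave the denominator alone. Infusion reactions are divided by administrations received. Only optional time-to-event curves for selected signals censor at the end of the TEAE period.

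**Conclusion.** The point holds as a conflict within one rule, worth correcting before first-step lock. On the opening sentence, a double-blind patient last dosed at week 4 who never had the visit is reported with 28.1 weeks (24.1 if exposure stops at the cut-off) instead of 8.1 when t = 0, and more if randomised earlier. On the first-item test the figure stays at 8.1. The size rests on the literal reading, on at least one patient leaving without the visit, and on an accrual period that the documents do not state.

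The effect is confined to first-step exposure durations and to treatment and TEAE period ends. The primary analysis uses LDL-C values by analysis window regardless of adherence, and the efficacy treatment period in SAP 3.1.2 is defined from the last double-blind dose, so efficacy is not touched. These rules are also limited to the first step.

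**What to change.** Use one test throughout SAP 7. Define ongoing as: in the open-label period at the cut-off; neither completed nor prematurely discontinued study treatment according to the end-of-treatment e-CRF; and not dead, withdrawn or lost. Apply all three items to these patients only. For everyone else, with or without an end-of-treatment visit, use the actual last dose date and the standard period ends in SAP 4.6 and 4.8.1, capped at the cut-off. State that no patient is ongoing in the double-blind period.

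This costs about two sentences and one derivation flag, with no new data. SAP 1 allows revision before the first-step database lock. If the narrower test was always intended, the change only writes it down.

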4.6. Study Treatment Exposure and Compliance Variables

Study treatment exposure variables for infusions administered during the DBTP are listed below with associated definitions:

- Patient duration of double-blind study treatment exposure in weeks defined as: (last double-blind study treatment administration date +28 – first double-blind study treatment administration date +1)/7. Unplanned intermittent discontinuations in study treatment will be addressed on a case-by-case basis, since this is expected to be a rare occurrence.
- The total number of double-blind study treatment infusions by patient.

- The following categories will be used for treatment exposure intervals: ≥ 1 day and < 4 weeks, ≥ 4 weeks and < 8 weeks, ≥ 8 weeks and < 12 weeks, ≥ 12 weeks and < 16 weeks, ≥ 16 weeks and < 20 weeks, ≥ 20 weeks.

Study treatment exposure variables for infusions administered during the OLTP are listed below with associated definitions:

- Patient duration of open-label study treatment exposure in weeks defined as: (last open-label evinacumab treatment administration date +28 – first open-label evinacumab treatment administration date)/7. Unplanned intermittent discontinuations in study treatment will be addressed on a case-by-case basis, since this is expected to be a rare occurrence.
- The total number of open-label evinacumab treatment infusions by patient.
- The following categories will be used for treatment exposure intervals: ≥ 1 day and < 4 weeks, ≥ 4 weeks and < 8 weeks, ≥ 8 weeks and < 12 weeks, ≥ 12 weeks and < 16 weeks, ≥ 16 weeks and < 20 weeks, ≥ 20 weeks.

Study treatment exposure variables combining DBTP and OLTP are listed below for all patients who received evinacumab in the DBTP:

- Cumulative patient duration of evinacumab exposure in weeks defined as: double-blind treatment exposure plus open-label treatment exposure, regardless of unplanned intermittent discontinuations.
- Cumulative total number of evinacumab treatment infusions by patient defined as: total number of double-blind infusions plus total number of open-label infusions.
- The following categories will be used for cumulative patient treatment exposure intervals: ≥ 1 day and < 4 weeks, ≥ 4 weeks and < 8 weeks, ≥ 8 weeks and < 12 weeks, ≥ 12 weeks and < 16 weeks, ≥ 16 weeks and < 20 weeks, ≥ 20 weeks and < 24 weeks, ≥ 24 weeks and < 28 weeks, ≥ 28 weeks and < 32 weeks, ≥ 32 weeks and < 36 weeks, ≥ 36 weeks and < 40 weeks, ≥ 40 weeks and < 44 weeks, ≥ 44 weeks.

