5.6.1. Exposure to Investigational Product

Study treatment exposure in the DBTP and OLTP will be descriptively summarized for treatment duration and total number of infusions as described in Section 4.6. Treatment duration and total number of infusions will be summarized using the number of patients with data, mean, SD, Q1, Q3, median, minimum and maximum.

Additionally, evinacumab dosing exposure will be summarized cumulatively across the study, combining DBTP and OLTP for patients who received evinacumab in the DBTP.

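### SAP Section 7, read literally, ends the first-step open-label exposure of ongoing patients 28 days after the data cut-off

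*SAP*

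**What the plan says.** SAP Section 4.6 measures open-label exposure in weeks from the first open-label dose to "last open-label evinacumab treatment administration date +28", divided by 7. Of the interval bands it then sets, it says "The following categories will be used for treatment exposure intervals". They rise in 4-week steps; the top open-label band starts at 20 weeks and the top cumulative band at 44 weeks. Under SAP Section 5.6.1, for patients given evinacumab in the double-blind period, "evinacumab dosing exposure will be summarized cumulatively across the study".

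SAP Section 7 adds rules for the first-step analysis, for which "the common cut-off date is defined as date of the last week 24 visit". It carries over the methods and conventions of the other sections where applicable. A patient with no end-of-treatment visit by then "will be considered as ongoing and exposed up to the cut-off date". Two consequences drawn from that are "Their TEAE period and treatment period will end at the cut-off date" and "Their treatment duration will be derived by considering date of cut-off as last administration date". The next bullet treats infusion counts differently: "Analyses of number of administrations, and mean administration frequency will be performed up to the last administration reported in the e-CRF", again limited to the cut-off.

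**The concern.** The 28 days in Section 4.6 credit the dosing interval that follows a real infusion. The Section 7 rule puts a date that is usually not an infusion date into the same term of the formula, and nothing says the 28 days then fall away. The result runs four weeks beyond the date to which the rule's own lead-in says the patient is exposed.

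The exposure tables would also set a true infusion count beside a duration built on a substitute date. A patient with one open-label infusion could show up to 7.86 weeks, where Section 4.6 credits one infusion with 4.0. Two programmers could differ by 4.0 weeks per ongoing patient, depending on whether they keep the 28 days. Protocol Section 10.4.9.1 allows the first-step analysis to be used in the submission dossier, so these durations may be read outside the study team.

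**Working it through.** **Inputs.** The exposure formulas are in SAP Section 4.6 and the substitution rule and cut-off definition in SAP Section 7. Open-label doses are every 4 weeks from day 169 to day 309 (Protocol Section 7.1), and the end-of-open-label visit is on day 337 (Protocol Table 3).

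**Check of the formula on a completer.** (309 + 28 − 169)/7 = 168/7 = 24.0 weeks, the planned length of the open-label period. So the 28 days stand for the interval after the last real dose.

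**Set-up.** Let d be the cut-off date minus the first open-label dose date. For an on-schedule patient with the final visit still to come, d runs from 0 to 167, and doses fall at 0, 28, 56, 84, 112 and 140. Three durations are compared:

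- literal rule: (d + 28)/7
- last-dose convention: (last dose + 28)/7
- exposure through the cut-off day: (d + 1)/7

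| d | Literal | Last dose + 28 | Through cut-off day |
|---|---|---|---|
| 0 | 28/7 = 4.0 | 28/7 = 4.0 | 1/7 = 0.14 |
| 27 | 55/7 = 7.86 | 28/7 = 4.0 | 28/7 = 4.0 |
| 167 | 195/7 = 27.86 | 168/7 = 24.0 | 168/7 = 24.0 |

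**Size of the excess.**

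- The literal end date is 28 days (28/7 = 4.0 weeks) after the cut-off for every ongoing patient, whatever the dosing pattern. Counting the cut-off day itself as exposed, the excess is 27/7 = 3.86 weeks.
- Against last dose + 28, the excess is (d − last dose)/7. With exact 28-day dosing this is 0 to 27/7 = 3.86 weeks, averaging 13.5/7 = 1.93 if every cut-off day is equally likely.
- Off schedule it can be larger. Protocol Section 7.1 allows ±7 days and skipped doses. The gap since the last dose can reach 28 + 7 − 1 = 34 days (4.86 weeks) with a late next dose, 28 + 14 − 1 = 41 days (5.86 weeks) if the previous dose was also early, and 56 − 1 = 55 days (7.86 weeks) after one skipped dose.
- The literal value passes 24.0 weeks for d = 141 to 167, which is 27 cut-off days.

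**Cumulative exposure, evinacumab throughout.** Double-blind exposure is (140 + 28 + 1)/7 = 169/7 = 24.14 weeks. At d = 167 the literal total is (169 + 195)/7 = 52.0 weeks, against (169 + 168)/7 = 48.14 for the full course.

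**Exposure bands, on schedule.**

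- Open-label, against last dose + 28: no change on any of the 168 days, because both values stay in the same 4-week band.
- Cumulative, against last dose + 28: the convention gives 197 + last dose in days, one day above a band boundary. The literal rule gives 197 + d and reaches the next boundary when d is 27 days past a dose. That moves the band at d = 27, 55, 83 and 111, so 4 of 168 days. At d = 139 and 167 both values are already in the top band.
- Open-label, against exposure through the cut-off day: the literal rule sits one band higher on 27 days in each of five bands, 135 of 168 days.

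**The case against.** The best defence is that the duration sentence is there to implement its lead-in, that patients are exposed up to the cut-off, and that conventions from other sections carry over only where applicable. A programmer could decide that an interval credited after a real infusion does not apply to a substitute date, and drop the 28 days. That may be what was meant, but no sentence says so, and the substituted term is exactly the one to which Section 4.6 adds 28.

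Other parts of the defence stand and limit the point:

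- Passing the cut-off is not in itself foreign to the SAP. On schedule, last dose + 28 also ends 1 to 28 days after it. So a reader should not infer that every ongoing patient is four weeks above the SAP's usual convention; on schedule that excess is 0 to 3.86 weeks.
- The sentence ending the treatment period at the cut-off is weak evidence. In SAP Section 4.8.1 that term is an adverse event window running to last dose + 35 days, not the exposure duration. The contradiction is with the lead-in.
- The 135-day band count depends on measuring exposure through the cut-off day. Against the SAP's own convention, open-label bands do not move.
- The lowest band, under 4 weeks, is empty for ongoing patients under the literal rule. This is no separate fault of Section 7: the 28 days in Section 4.6 already give any dosed patient at least 4.0 weeks.

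**Conclusion.** The rule is wrong as written, and the consequence is minor. Applied literally, it ends exposure 4.0 weeks after the date to which the same bullet says patients are exposed. The 4.0 weeks need no assumption about dosing. The 0 to 3.86 weeks, the maxima of 27.86 and 52.0 weeks and the band counts assume dosing exactly every 28 days and a cut-off before the day 337 visit. The documents do not say how many patients will be ongoing, so the effect on group summaries cannot be sized.

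A reader might infer that efficacy or safety conclusions are at risk. The documents do not support that. The efficacy analyses do not use exposure duration. Adverse event percentages use the safety analysis set as denominator (SAP Section 5.8.1), and the infusion-reaction rate divides by the number of administrations (SAP Section 5.8.2). Double-blind exposure is untouched because the cut-off is the last week 24 visit, and the second step recalculates from actual last doses.

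**What to change.** In SAP Section 7, replace the duration sentence with: *For ongoing patients, open-label treatment duration in weeks = (cut-off date − first open-label administration date + 1)/7; the +28 days of Section 4.6 is not added.*

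This follows the lead-in, including when a dose is late. It credits one day (0.14 weeks) to a patient first dosed on the cut-off date and gives 168/7 = 24.0 weeks at open-label day 168, which matches a full course.

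The cost is one sentence, with no new data, no protocol change and no effect on efficacy or adverse event incidence. There is one small drawback. Patients who have discontinued keep last dose + 28, so the two groups are credited differently. With one infusion and a cut-off six days later, an ongoing patient gets 7/7 = 1.0 week and a discontinued patient 28/7 = 4.0 weeks. Truncating the discontinued patients' duration at the cut-off as well would remove most of that difference; otherwise a table footnote should state it.
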